#### **Efficacy Analyses:**

Descriptive statistics by study visit will be displayed for:

- Proportion of patients with a CGI-I score of "very much improved" or "much improved" from baseline
- Change from baseline in the SDS
- Change from baseline in patients' quality of sleep score using the PROMIS Sleep Disturbance scale
- Change from baseline in BDI-II total score
- Change from Visit 5 to Visit 6 in PCL-S total score

## Pharmacogenomic Analyses:

Potential genetic determinants of treatment response will be examined by the assessment of genetic variants in relation to treatment outcome. A blood sample will be obtained from patients who have signed a separate informed consent form for the pharmacogenomic analyses. The blood sample can be obtained as soon as the patient has agreed to be tested and has signed the separate informed consent form; i.e., the blood draw is not tied to any specific study visit, hence it can be obtained at any time.

The first step of the pharmacogenomic analyses will involve exome sequencing and analysis for allelic polymorphisms related to treatment response to TNX-102 SL. It is presumed that unused sample will be stored up to fifteen years, and potentially utilized to develop a pharmacogenomic test for determining likelihood of treatment response to TNX-102 SL.

## LIST OF ABBREVIATIONS AND DEFINITIONS OF TERMS

The following abbreviations and specialist terms are used in this study protocol.

Abbreviation or Specialist Term	Explanation
AE	Adverse Event
ALT	Alanine Aminotransferase
AST	Aspartate Aminotransferase
BDI-II	Beck Depression Inventory–II
BMI	Body Mass Index
BUN	Blood urea nitrogen
CFR	Code of Federal Regulations
CGI-I	Clinical Global Impression- Improvement from Initiation of Treatment
CK	Creatinine Kinase
CoC	Certificate of Confidentiality
CRF	Case Report Form
CRO	Contract Research Organization
C-SSRS	Columbia Suicide Severity Rating Scale
CYP3A4	Cytochrome P450 subtype 3A4
e.g.	Exempli gratia (for example)
EC	Ethics Committee
ET	Early Termination
FDA	Food and Drug Administration
GCP	Good Clinical Practice
GLP	Good Laboratory Practice
HC1	Hydrochloride
HIPAA	Health Insurance Portability and Accountability Act
i.e.	id est (that is)
ICF	Informed Consent Form
ICH	International Council on Harmonisation
IND	Investigational New Drug
IRB	Institutional Review Board
МСН	Mean corpuscular hemoglobin

Abbreviation or Specialist Term	Explanation
MCHC	Mean corpuscular hemoglobin concentration
MCV	Mean corpuscular volume
MedDRA	Medical Dictionary for Regulatory Activities
Mg	Milligram(s)
N, n	Number (of patients)
NA	Not applicable
NEAE	Newly Emergent Adverse Event
PCL-S	PTSD Checklist-Specific Version
PROMIS	Patient-Reported Outcome Measurement Information System
PTSD	Posttraumatic Stress Disorder
RBC	Red blood cell
SAE	Serious Adverse Event
SAP	Statistical Analysis Plan
SD	Standard deviation
SDS	Sheehan Disability Scale
SL	Sublingual
SNRIs	Serotonin–norepinephrine reuptake inhibitors
SOC	System Organ Class
SOP	Standard Operating Procedures
SPI	Safety Planning Intervention
SSRIs	Selective serotonin reuptake inhibitors
TNX-102 SL	Cyclobenzaprine HCl sublingual tablets
Tonmya	FDA conditionally accepted proposed proprietary name for TNX-102 SL for the treatment of PTSD
US	United States
VA	Veteran's Administration
WBC	White blood cell
WHO	World Health Organization

## 4. INTRODUCTION

The background information provided in the lead-in study protocol and the most current TNX-	-
102 SL Investigator's Brochure is relevant to this extension study.	

## 5. TRIAL OBJECTIVES AND PURPOSE

## 5.1. Primary Objective

The primary objective of the study is to evaluate the long-term safety of TNX-102 SL taken daily at bedtime over an additional 40 to 52 weeks in patients with PTSD who have participated in a double-blind lead-in HONOR study and possibly a 12-week open-label extension study P303.

## 5.2. Secondary Objectives

The secondary objective of the study is to evaluate the long-term effect of TNX-102 SL taken daily at bedtime over an additional 40 to 52 weeks in patients with PTSD who have participated in a double-blind lead-in HONOR study and possibly a 12-week open-label extension study P303.

## 6. INVESTIGATIONAL PLAN

## 6.1. Overall Study Design

This is a 40 to 52-week, multicenter, open-label extension study designed to establish long-term safety exposure and to examine the long-term effect with daily bedtime dosing of TNX-102 SL 5.6 mg (2 x 2.8mg tablets) in patients with PTSD. This study will be conducted at approximately 35 sites in the United States (US).

Patients who have either: (a) completed the double-blind lead-in study and complete, *or are active (at the time of study discontinuation)* in the 12-week open-label extension study, P303; or (b) are currently enrolled in the double-blind lead-in study (HONOR study) that has been discontinued due to results of an interim analysis, will be eligible. For Track A patients, this extension study consists of 5 in-clinic visits, including the Screening/Baseline visit and visits after 7, 16, 28 and 40 weeks of treatment (Visits 3-6). There will also be a telephone visit after two weeks of treatment (Visit 2) for patients enrolling from the double-blind lead-in study, P301/HONOR. The total treatment duration of this study will be 40 weeks for patients enrolled under Track A criteria, and 52 weeks for patients enrolled under Track B criteria. Therefore, the maximum total duration of continuous treatment with TNX-102 SL could be approximately 64 weeks for those patients assigned to TNX-102 SL in the lead-in HONOR study who then also completed the 12-week open-label extension study P303.

For patients enrolling from the open-label extension study, P303, there is no need to repeat assessments at Visit 1 for this study, if the patient enrolls and initiates study treatment within fourteen days of completing the 12-week open-label extension study P303. For patients who are active in the double-blind lead-in study, P301/HONOR, all Baseline procedures and assessments will be completed at Visit 1.

After the patient has participated in the lead-in HONOR study or the open-label extension study, P303, and has consented to participate in this open-label extension study, patients will be dispensed a 7-week supply of open-label TNX-102 SL tablets (3 bottles) and will be instructed to take 2 tablets of study drug sublingually daily at bedtime, starting on the evening of Visit 1. A phone visit will be completed after 2 weeks of treatment for patients enrolling from the double-blind lead-in study, P301/HONOR. All patients will return to the study center for safety and efficacy assessments at Weeks 7, 16, 28, and 40 (or early termination). Patients enrolled under Track B criteria will continue to dose for an additional 12 weeks and have the last study visit at Week 52. Patients will return their TNX-102 SL medication (including empty bottles) at these visits. Patients will also receive a 9-week supply of TNX-102 SL (4 bottles) at the Week 7 visit, and a 12-week supply (5 bottles) at the Week 16, 28 and 40 (Week 40 for Track B patients only) visits. Patients will be allowed to take other medications deemed appropriate by their health care providers to manage their PTSD and other conditions, including currently approved PTSD therapies. See Section 8.5 for a discussion of allowed concomitant treatments.

The study timeline and events schedule is provided in Appendix 1.

## **6.2.** Number of Patients and Treatment Assignment

Up to 200 patients will enroll into this study. Eligible patients will either have completed a double-blind lead-in HONOR study and participated in a 12-week open-label study P303 or will

have been currently enrolled in a double-blind lead-in HONOR study when that study was discontinued due to results of an interim analysis.

All patients will be assigned to TNX-102 SL, 5.6 mg regardless of which treatment arm they were randomized to in the lead-in HONOR study.

## 6.3. Study Endpoints

## **6.3.1.** Safety

Safety will be assessed by:

- Adverse events (AEs) and serious AEs (SAEs) throughout the entire duration of the study, including assessment of AEs involving the oral cavity
- Change from baseline in clinical laboratory test results
- Changes from baseline indicative of increased suicidal ideation or behavior as assessed by the Columbia Suicide Severity Rating Scale (C-SSRS)
- Change from baseline in Beck Depression Inventory-II (BDI-II)
- Changes from baseline in vital signs and weight
- Track A patients only: Change from Visit 5 to Visit 6 in PTSD Checklist-Specific Version (PCL-S)
- Track B patients only: Change from Visit 5 to Visit 7 in PTSD Checklist-Specific Version (PCL-S)

## 6.3.2. Efficacy

Descriptive statistics by treatment and study visit will be displayed for a number of efficacy endpoints including:

- Proportion of patients with a Clinical Global Impression-Improvement from Initiation of Treatment (CGI-I) score of "very much improved" or "much improved" from baseline
- Change from baseline in the Sheehan Disability Scale (SDS)
- Change from baseline in patients' quality of sleep using the Patient-Reported Outcome Measurement Information System (PROMIS) Sleep Disturbance scale
- Change from baseline in BDI-II score
- Change from Visit 5 to Visit 6 in PTSD Checklist-Specific Version (PCL-S)

## 7. SELECTION AND WITHDRAWAL OF PATIENTS

#### 7.1. Informed Consent

A potential patient may be screened for eligibility only after the nature of the study, its purpose, and any other information relevant to the patient's decision to participate have been explained to him or her and the patient has voluntarily confirmed his or her willingness to participate. The investigator will determine the potential patient's suitability for the study by interviewing the

patient and by reviewing the patient's experience in the double-blind lead-in HONOR study and/or 12-week open-label extension study P303.

Informed consent is documented by means of a written, signed, and dated informed consent form (ICF). Separate written, signed informed consent must be obtained if the patient is to participate in the optional pharmacogenomic assessment. Additional information is provided in Section 14.3.

## 7.2. Inclusion Criteria

- 1. The patient has either a) completed the double-blind lead-in study and completed or is active (at the time of study discontinuation) in the 12-week open-label extension study (P303), or b) is currently enrolled in the double-blind lead-in study that was discontinued due to results of an interim analysis, and is judged by the investigator as reasonably compliant, with at least 60% compliance with study medication usage (based on drug accountability).
- 2. The patient has provided written informed consent to participate in this extension study. *Note:* Separate written, signed informed consent will be required if the patient is to participate in the optional pharmacogenomic assessment. A decision not to participate in the optional pharmacogenomic testing will not affect the patient's eligibility for the main study.
- 3. The patient met all prior inclusion and exclusion requirements for the double-blind leadin study, or the site received medical monitor approval for the patient to remain in the lead-in study after the retrospective discovery of an entry violation that did not pose any threat to the patient's safety or well-being.
- 4. During the course of the lead-in study or 12-week open-label extension study, the patient has had no intervening medical conditions including pregnancy, clinically significant increase in suicidal ideation (plan or intent) or significant worsening of depression, newly arising clinically significant abnormal laboratory tests, or any clinically significant, uncontrolled, or unstable medical or surgical condition that could affect the patient's ability to participate in the study or potentially compromise the patient's well-being during the study.
- 5. The patient does not require treatment with a potent (strong) cytochrome P450 subtype 3A4 (CYP3A4) inhibitor, or St. John's wort.
- 6. The patient is willing to refrain from use of all other formulations of cyclobenzaprine for the duration of the study.
- 7. The patient is willing to refrain from use of monoamine oxidase inhibitors for the duration of the study.
- 8. Female patients of childbearing potential continue to agree to practice one of the medically acceptable methods of birth control detailed in the lead-in study.

## 7.3. Patient Exclusion Criteria

There are no exclusion criteria for this study.

## 7.4. Withdrawal Criteria

There are no pre-specified withdrawal criteria for this study. In accordance with the Declaration of Helsinki, human patients have the right to withdraw from the study at any time for any reason. The investigator and Tonix also have the right to remove patients from the study. Additional information regarding withdrawal or discontinuation of patients is described in detail in Section 9.6.

## 8. STUDY DRUG MATERIALS AND MANAGEMENT

## 8.1. Study Drug Packaging, and Labeling and Storage

The study medication bottles will be labeled minimally with the following information: study number TNX-CY-P306 (P306), sponsor name and address, bottle number, drug name, quantity, storage conditions, usage instructions, and caution statements for investigational new drug, i.e., Caution: New Drug Limited by United States Law to Investigational Use, and Keep Out of Reach of Children and Pets.

Each study medication bottle will contain 40 tablets. Since the patient will dose with two tablets sublingually each night, three bottles will be dispensed to each patient at Visit 1/Baseline. Four bottles will be dispensed at Week 7 and five bottles at Weeks 16, 28 and 40 (Week 40 for Track B patients only); this will provide the patient with enough study drug between visits, plus additional tablets to cover loss and/or visit window variability. The patient should be instructed to take all the tablets in one bottle before opening another bottle. The patient should be instructed to keep this study medication in a safe location out of extreme environmental conditions and out of the reach of children and pets, and that this medication is not to be taken by any individual other than the study patient. Each patient will also be instructed that they will be expected to return all bottles and all unused study medication at each clinic visit; unused medication will be counted to assess compliance with study drug treatment.

Storage of the study drug at the investigational site should be under locked and secure conditions with limited staff access. Study drug should be stored at 20-25°C/68-77°F in a temperature/humidity-monitored room; however, brief excursion (15-30°C/59-86°F) as defined in the Study's Reference Manual (IP Receipt and Storage) is permitted without sponsor's approval.

## **8.2.** Dosing Instructions

Patients will be instructed to take two (2) TNX-102 SL 2.8 mg tablets sublingually, placed simultaneously under the tongue, each evening at bedtime starting on evening of Day 0 and continuing without interruption for 40 to 52 weeks. The study drug should be taken at bedtime after teeth brushing and other oral care has been completed. The mouth/sublingual area should be moist at the time of dosing, so the patient should drink a few sips of water prior to dosing, especially if prone to dry mouth. Patients will be instructed to place the two TNX-102 SL 2.8 mg tablets under their tongue and keep them there until they have dissolved. They should not swallow, crush or chew the tablets. Patients should not eat or drink (or chew gum) for at least 15 minutes after dosing, and preferably not until morning. Patients will be reminded that only two (2) tablets are allowed per day. Note: In the event that the patient misses a dose, instruct the patient to continue dosing with two (2) tablets the next evening; i.e., they should not take more to make up for the missed dose.

Patients should also be reminded to keep the desiccant in the bottle after opening and to screw the cap on tightly after dosing.

## **8.3.** Dispensing Instructions

Each enrolled patient will be assigned 3, 4 or 5 bottles of TNX-102 SL at each dispensing visit. Bottles of TNX-102 SL tablets are numbered and will be supplied to sites as open stock. Patients are reminded to open and use one bottle of TNX-102 SL tablets at a time.

## 8.4. Release of Clinical Study Supplies to the Investigator

Tonix or Tonix's designee's standard operating procedures (SOP) for releasing clinical trial supplies to the site will be followed.

#### **8.5.** Concomitant Medications

Many of the restrictions in the lead-in study related to concomitant medications and traumafocused psychotherapy will be relaxed. Therefore, patients may utilize antidepressants, mood stabilizers, anticonvulsants, benzodiazepines, stimulants, and opioids, if needed, unless specifically excluded as outlined below. Patients may take medications to help them sleep, per the judgment of the investigator.

Any concomitant medications or other treatments, including dietary supplements, must be recorded in the patient's medical record and case report form along with the indication, dose and dates of treatment.

The following medications are specifically excluded during the study and patients must agree to refrain from use of these medications during the study:

- Any other forms of cyclobenzaprine (FLEXERIL®, AMRIX®, FEXMID®, or generic equivalents) continue to be specifically excluded during the study and patients must agree to refrain from use of these medications during the study.
- Monoamine oxidase inhibitors (tranylcypromine, phenelzine, isocarboxazid, and selegiline)
- Cytochrome P450 3A4 inhibitors (strong ones only) (refer to Appendix 2 for a list).
- St. John's wort

NOTE: Patients initiating treatment with antidepressants, tramadol or other opioids, triptans, or any other serotonergic medication should be cautioned about the possibility of serotonin syndrome which has been reported in patients receiving cyclobenzaprine with selective serotonin reuptake inhibitors (SSRIs), serotonin–norepinephrine reuptake inhibitors (SNRIs) and other serotoninergic agents. (See Appendix 3, AMRIX® Package Insert, Warnings Section). The patient should be instructed to call the clinic immediately in the event of any of the warning signs or symptoms of serotonin syndrome, as outlined in the informed consent. The investigator should carefully review the patient's complete list of medications when considering new treatments and the site should ask the patient to call the site (or return for an unscheduled clinic visit) within one week after adding a new serotonergic therapy (or increasing the dose of a prior treatment).

## 8.6. Study Drug Accountability and Reconciliation

All patients will be expected to bring their bottles of study medication with them to study visits. The site staff will inspect the medication bottles and perform a count of the tablets remaining in the bottles and the number of tablets that the patient should have returned (based on the number of days since the previous visit). The number of tablets dispensed, the number returned, and the number expected to be returned will be recorded in the patient's record. An assessment of medication adherence should be done by the study staff to ensure that the patient understands all dosing instructions and is taking the medication as prescribed. If it is found that the patient is not taking the study medication as prescribed, the patient will be re-counseled on correct administration, and this should be noted in the patients' record, and discussed with the medical monitor, if necessary.

If the patient fails to return all unused study drug as expected, the patient should be questioned regarding the reason for the lower than expected tablet number and about potential misuse, abuse or diversion. In situations where more than 2 tablets per week cannot be accounted for, the investigator will be asked to evaluate the situation, and a written summary should be added to the source and entered onto the case report form (CRF). In addition, the medical monitor should be contacted any time a patient requests replacement medication for any reason (e.g., loss of bottles or damage to study drug). Situations where replacement drug is requested, or when more than 2 tablets per week cannot be accounted for, should be recorded as deviations.

All study medication, including partial and empty bottles, must be maintained at the study site until Tonix or its designee verifies drug accountability and provides instruction for the destruction or the return of the investigational product to the Sponsor's drug distribution depot.

Tonix or their designee will perform drug accountability which entails reconciliation between the amount of drug shipped to the study site, study drug assigned and dispensed to the patient (including returned unused assigned study drug), and study supplies that were never dispensed and/or assigned to patients.

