Compliance will be summarized with descriptive statistics by treatment arm. The number and percentages of participants within certain categories of compliance e.g. <50%, 50% to <70%, 70% to <100%, >100% will be presented. Compliance between 70% to 114% will not be considered a protocol deviation. Tablet counts, calculation of compliance overall and by visit, and participant-reported reasons for all tablet discrepancies at all visits will be presented in a listing.

In addition, participants with significant over-usage or otherwise unaccounted-for missing tablets resulting in >114% compliance for any visit (e.g., failure to return >8 tablets per 4 week interval) will be summarized by visit and overall. These listings will include both the participant-reported reason for the discrepancy plus the investigator's assessment of potential abuse, misuse or diversion. Clinically significant drug accountability discrepancies associated with missing medication, loss of drug, or cases in which the PI confirms concern over drug abuse, misuse or diversion, will be examined and discussed in the CSR.

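### When a visit falls late in its window, the over-use tier (more than 2 tablets per week; >114%) cannot be reached even if every spare tablet is missing, so its counts contain forced zeros.

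*Protocol*

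**What the plan says.** Protocol 8.1 fixes the supply. "Each study medication bottle will contain 40 tablets", "the patient will dose with two tablets sublingually each night", and "three bottles will be dispensed to each patient at Visit 1/Baseline". After that, "Four bottles will be dispensed at Week 7 and five bottles at Weeks 16, 28 and 40", the Week 40 supply being for Track B only. The section says the extra tablets are there for loss and for variation in visit timing, and it asks for all unused drug back at every clinic visit.

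Protocol 8.6 has staff count what is left and compare it with "the number of tablets that the patient should have returned (based on the number of days since the previous visit"). It then sets two tiers. At any shortfall, "the patient should be questioned regarding the reason for the lower than expected tablet number and about potential misuse, abuse or diversion". Above a rate there is more: "In situations where more than 2 tablets per week cannot be accounted for, the investigator will be asked to evaluate the situation", with a written summary in source and CRF and a recorded deviation. Any request for replacement drug goes to the medical monitor and is also a deviation.

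SAP 11.2 treats a shortage of more than 8 tablets per 4-week assessment period as a deviation, says that compliance from 70% to 114% is not one, and summarises over-use or missing tablets "resulting in >114% compliance for any visit (e.g., failure to return >8 tablets per 4 week interval"). It also plans a >100% compliance category and a listing of tablet counts and patient-reported reasons for all discrepancies. The same section refers to a double-blind phase, which P306 does not have.

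**The concern.** The escalation tier is a rate, but the drug available to go missing is a fixed stock that shrinks with time. Expected use grows by 2 tablets a day, so each day of delay takes 2 tablets from the spare and adds 2/7 of a tablet to the allowance. Past some interval length the whole spare is smaller than the allowance, and no count of returned tablets can trigger the tier.

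The tier decides which shortages get a written investigator evaluation, which are recorded as shortage deviations, and which enter the SAP's over-use summary with the investigator's view on abuse, misuse or diversion. If some intervals cannot contribute a positive, a low count in that summary partly reflects visit timing. The planned tables give the reader no way to tell how much.

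**Working it through.** **Inputs.** Tablets dispensed D = 120, 160, 200, 200, 200 (3, 4, 5, 5, 5 bottles of 40; Protocol 8.1). Dose: 2 a day. Visit days 49, 112, 196, 280 and 365, each ±7 (Protocol Appendix 1). The permitted intervals are therefore 42–56, 49–77, 70–98, 70–98 and 71–99 days.

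**The plan's own figures.** Bottles needed: 98/40 = 2.45, 126/40 = 3.15 and 168/40 = 4.2, which round up to 3, 4 and 5 as stated. The 114% limit: 4 weeks is 56 tablets, and (56 + 8)/56 = 114.3%.

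**Largest countable shortage.** Over d days the expected return is D − 2d. If nothing comes back, that whole spare is the shortage.

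**Protocol trigger.** More than 2 per week means more than 2d/7. It is reachable only if D − 2d > 2d/7, that is d < 7D/16 = 52.5, 70 and 87.5. It is unreachable from 53, 70 and 88 days.

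**SAP trigger.** D/(2d) > 1.14, that is d < D/2.28 = 52.6, 70.2 and 87.7. It is unreachable from 53, 71 and 88 days. The two rules differ only at exactly 70 days on 160 tablets: 20 missing against more than 20, but 160/140 = 114.3%.

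**Spare against protocol trigger (interval length in brackets):**

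| Visit | On target | This visit +7, previous on target | Previous −7, this +7 |
|---|---|---|---|
| 3 | 22 vs >14 (49 d) | 8 vs >16 (56 d) | not applicable |
| 4 | 34 vs >18 (63 d) | 20 vs >20 (70 d) | 6 vs >22 (77 d) |
| 5, 6 | 32 vs >24 (84 d) | 18 vs >26 (91 d) | 4 vs >28 (98 d) |
| 7 | 30 vs >24.3 (85 d) | 16 vs >26.3 (92 d) | 2 vs >28.3 (99 d) |

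The tier can fire in every cell of the first column. Under the protocol rule it can fire in none of the others. With the previous visit on target, the protocol trigger is lost from +4 days at Visit 3, +7 at Visit 4, +4 at Visits 5 and 6, and +3 at Visit 7. At Visit 4 the SAP rule is lost only when the two visits together stretch the interval by 8 days or more.

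**Examples with all bottles returned empty.** 120 tablets over 53 days: 120/106 = 113.2%. 160 over 71 days: 160/142 = 112.7%. 200 over 88 days: 200/176 = 113.6%. None exceeds 114%.

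**How often.** The documents do not give the distribution of visit days. If days were independent and uniform within ±7 (an assumption), the protocol tier would be unreachable in 4/15 = 27% of Visit 3 intervals, 36/225 = 16% at Visit 4 (SAP rule 28/225 = 12%), 66/225 = 29% at Visits 5 and 6, and 78/225 = 35% at Visit 7. With visits on target the share is zero.

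**The case against.** The best reply is that a rate threshold which ignores a sub-threshold rate is doing its job. In the 88-day example, 24 tablets are missing over 12.6 weeks, about 1.9 a week. Limited supply at a late visit also caps over-use physically, and the spare is meant to absorb loss and timing. This stands as a defence of having a rate. It does not make the summary interpretable when some intervals could not have contributed to it.

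Four stronger readings are tempting, and the documents do not support them:

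- **That the tier fails at the later scheduled visits.** It does not. It can fire on every target day, and the problem is confined to visits late within their window.
- **That late attenders are exempt, or that these shortages leave no trace.** Under Protocol 8.6 any shortfall leads to questioning about misuse, and a replacement request is a deviation. SAP 11.2 has the >100% category and the listings, and sends cases where the investigator confirms concern to the study report with no 114% condition.
- **That this summary is the only evidence on abuse.** SAP 10.1 and 12.2 tabulate abuse-related adverse events separately from tablet counts.
- **That the SAP already implies a limit of 8 tablets per interval.** Its figure is 8 per 4 weeks. Eight per 12 weeks would be three times stricter, would conflict with the 70–114% tolerance, and would still be unreachable at 56, 76–77 and 96 or more days.

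**Conclusion.** The point holds in a limited form. One escalation tier, expressed as a rate over 4-week periods that P306 does not have, is unattainable for in-window intervals of at least 53 days (7-week supply), 70 or 71 days (9-week) and 88 days (12-week). Those intervals contribute forced zeros to the investigator-evaluation and shortage-deviation counts and to the >114% over-use summary. The lower tier, the replacement rule, the >100% category and the listings are unaffected. However, the >100% category pools one missing tablet with a whole missing spare, and a listing of patients' reasons is not the investigator's assessment.

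The thresholds are exact arithmetic under these assumptions: the rate is averaged over the interval, expected use (and the SAP's assigned number of tablets) is 2 per day since the previous visit, nothing is carried over, no replacement bottles are issued, and bottles are returned and counted. Tablets withheld after missed doses would not show in a count by days, so the spare is the most this method can detect. How many intervals are affected depends on actual visit dates. The effect is on how the misuse data can be read, in a descriptive study.

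**What to change.** In SAP 11.2:

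1. Add a table of missing tablets for each counted interval, as a number and as a percentage of tablets expected back (dispensed minus 2 × days). Show the expected number beside the percentage, since it can be as low as 2 to 8 at the latest in-window visits.
2. Identify intervals in which no expected spare was returned, separately from those dropped because no bottles came back.
3. Give, as the denominator of the over-use summary, the number of counted intervals in which >114% was attainable (dispensed/(2 × days) > 1.14).
4. Replace the 4-week and double-blind-phase wording with terms that fit this study.

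Reconcile the Protocol 8.6 trigger and the SAP's 70–114% tolerance with the 7-, 9- and 12-week supplies. If a per-interval count is adopted, present it as a new choice, not as the SAP's existing figure. The protocol estimated last patient completion in September 2019 and the SAP cites a 2023 source, so a change to 8.6 may come too late to affect conduct. The SAP additions would still be useful.

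The cost is one extra table from counts that 8.6 already requires, some wording, and somewhat more discrepancies to describe in the report.
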